We would like to know how confident you are in doing certain activities. For each of the following questions, please choose the number that corresponds to your confidence that you can do the tasks regularly at the present time.

1. How confident do you feel that you can keep the fatigue caused by your disease from interfering with the things you want to do?	not at all confident	1	2	3	 4	5	6	7	8	9	 10	totally confident
2. How confident do you feel that you can keep the physical discomfort or pain of your disease from interfering with the things you want to do?	not at all confident	1	1 2] 3	1	5	 6	 7	8	9	- 10	totally confident
3. How confident do you feel that you can keep the emotional distress caused by your disease from interfering with the things you want to do?	not at all confident	- 1	1 2	3	4	5	6	7	 8	9	 10	totally confident
4. How confident do you feel that you can keep any other symptoms or health problems you have from interfering with the things you want to do?	not at all confident	- 1	1 2	3	1 4	 5	6	7	8	9	 10	totally confident
5. How confident do you feel that you can do the different tasks and activities needed to manage your health condition so as to reduce your need to see a doctor?	not at all confident		2	3	4	5	6	7	8	9	 	totally confident
6. How confident do you feel that you can do things other than just taking medication to reduce how much your	not at all	 1	1 2	 3	 	 	 	 7	 8		 10	totally confident

SCORE					

illness affects your everyday life?

Frail2Fit study

Semi-structured interview schedule for volunteers

- 1. Tell me your views about being physically active in general.
 - a. Explore general perception on physical activity
 - b. What are the potential benefits?
 - c. Any potential harm?
- 2. In your view, what are the things/factors that could discourage older people to be more active?
 - a. Explore environmental factors, motivation, cost, accessibility, fear of injury/falls and any other additional factors
- 3. What are the things/factors that could encourage older people to be more active?
 - a. Explore environment, social support, interest, accessibility and any other additional factors
 - b. Explore types of physical activity which older people are more likely to engage with, including frequency, and duration.
- 4. What are your general views about diet / nutrition for older people?
 - a. Explore general perception on nutrition and eating
 - b. What are the potential benefits for older adults following a healthy eating pattern?
 - c. Are there any drawbacks, or disadvantages from altering diet / nutrition?
- 5. In your view what are the things that could encourage older people to eat healthily?
 - a. Explore food acquisition and preparation
 - b. Explore nutritional knowledge, environment, social support, interest
 - c. Explore types of foods that older people may prefer to eat
- 6. In your view what discourages older people from eating healthily?
 - a. Explore social and environmental factors e.g., cost of food, lack of help in preparing meals
 - b. Explore appetite, taste preferences and dietary habits
- 7. What motivated you to volunteer for the role?
- 8. What are your views on the use of trained volunteers to deliver group exercise and nutrition support to older people in the community?
 - a. Can you describe your experience with these classes? Any advantages or disadvantages?

- b. What was good about these groups? And what things do you think need improvement?
- c. What were the benefits?
- d. Were there negative experiences?
- 9. In your view, what has it been like as a volunteer encouraging participants to be more active?
 - a. Explore if it worked for some but not others, including reasons for this.
- 10. In your view, what has it been like as a volunteer delivering the nutrition wheel and encouraging participants to eat healthily?
 - a. Explore if it worked for some but not others, including reasons for this.
- 11. What were your experiences with the volunteer training?
 - a. Explore training content and timing
 - b. Explore opinions regarding training resources, such as booklets and videos
 - c. Explore if any improvements are needed for volunteer training
 - d. Explore their perceptions of available support e.g., support given, impact on confidence levels, availability of peer support
- 12. Do you have any suggestions or comments about the intervention?
 - a. Explore things that went well
 - b. Explore things that could be improved
- 13. What were your experiences with delivering the support online?
 - a. Explore any barriers to accessing, or using the online intervention e.g., tech knowledge, general perceptions of using technology, any misconceptions regarding online platforms, visibility and sound during sessions
 - b. Explore the things that helped / facilitated use of online tech
- 14. In your opinion, how could these volunteer-led sessions be continued and extended to other clubs?
 - a. Explore participants views on barriers and facilitators to the implementation of the intervention in other settings
- 15. How can we improve the volunteering experience for future volunteers in this intervention?
 - a. Explore factors to aid retention and recruitment of others

Frail2Fit study

Semi-structured interview schedule for patients

- 1. Since being discharged from hospital how have things been going for you at home?
 - a. Could you explain what a typical day is like for you? (Build rapport and understand what life is like for them)
 - b. Explore functional capacity
 - c. Explore meaningful activities and general day to day motivation
 - d. Explore any concerns or barriers to recovery post-discharge
- 2. Tell me your views about being physically active in general.
 - b. Explore general perception on physical activity
 - c. What are the potential benefits?
 - d. Any potential harm?
- 3. In your view, what are the things/factors that could discourage older people to be more active?
 - a. Explore environmental factors, motivation, cost, accessibility, fear of injury/falls
- 4. What are the things/factors that could encourage older people to be more active?
 - a. Explore environment, social support, interest, accessibility
 - b. Explore types of physical activity which older people are more likely to engage with, including frequency, and duration.
- 5. What are your general views about diet / nutrition? What is your eating and diet like?
 - d. Explore general perception on nutrition and eating
 - e. What are the potential benefits of following a healthy eating pattern?
 - f. Are there any drawbacks, or disadvantages from altering diet / nutrition?
- 6. In your view what are the things that could encourage older people to eat healthily? What helps you to eat more healthily?
 - d. Explore food acquisition and preparation
 - e. Explore nutritional knowledge, environment, social support, interest
 - f. Explore types of foods that older people may prefer to eat
- 7. In your view what discourages older people to eat healthily? What stops you eating more healthily?
 - c. Explore social and environmental factors e.g., cost of food, lack of help in preparing meals
 - d. Explore appetite, taste preferences and dietary habits

- 8. What are your views on the use of trained volunteers to deliver group exercise and nutrition support to older people in the community?
 - a. Can you describe your experience with these exercise and nutrition sessions? Any advantages or disadvantages?
 - b. What was good about these groups? And what things do you think need improvement?
 - c. What were the benefits?
 - d. Were there negative experiences?
- 9. In your view, how effective were the trained volunteers at delivering the exercises and encouraging participants to be more active?
- 10. In your view, how effective were the trained volunteers at delivering the nutrition wheel and encouraging participants to eat healthily?
- 11. Do you have any suggestions or comments about the intervention?
 - a. Explore things that went well
 - b. Explore things that could be improved
- 12. What were your experiences with using the device and receiving the support online?
 - c. Explore any barriers to accessing, or using the online intervention e.g., tech knowledge, general perceptions of using technology, any misconceptions regarding online platforms, visibility and sound during sessions
 - d. Explore the things that helped / facilitated use of online tech
- 13. In your opinion, how could these volunteer-led sessions be continued and extended to other clubs?
 - c. Explore participants views on barriers and facilitators to the implementation of the intervention in other settings

Frail2Fit study

Semi-structured interview schedule for family members

- 1. Since being discharged from hospital how have things been going for your family member at home?
 - e. Could you explain what a typical day is like for them? (Build rapport and understand what life is like for them)
 - f. Explore functional capacity
 - g. Explore meaningful activities and general day to day motivation
 - h. Explore any concerns or barriers to recovery post-discharge
- 2. Tell me your views about being physically active in general.
 - e. Explore general perception on physical activity
 - f. What are the potential benefits?
 - g. Any potential harm?
- 3. In your view, what are the things/factors that could discourage older people to be more active?
 - a. Explore environmental factors, motivation, cost, accessibility, fear of injury/falls
- 4. What are the things/factors that could encourage older people to be more active?
 - c. Explore environment, social support, interest, accessibility
 - d. Explore types of physical activity which older people are more likely to engage with, including frequency, and duration.
- 5. What are your general views about diet / nutrition? What is your family member's eating and diet like?
 - g. Explore general perception on nutrition and eating
 - h. What are the potential benefits of following a healthy eating pattern?
 - i. Are there any drawbacks, or disadvantages from altering diet / nutrition?
- 6. In your view what are the things that could encourage older people to eat healthily? What helps your family member to eat more healthily?
 - g. Explore food acquisition and preparation
 - h. Explore nutritional knowledge, environment, social support, interest
 - i. Explore types of foods that older people may prefer to eat
- 7. In your view what discourages older people to eat healthily? What stops your family member eating more healthily?

- e. Explore social and environmental factors e.g., cost of food, lack of help in preparing meals
- f. Explore appetite, taste preferences and dietary habits
- 8. What are your views on the use of trained volunteers to deliver group exercise and nutrition support to older people in the community?
 - e. Can you describe your family member's experience with these exercise and nutrition sessions? Any advantages or disadvantages?
 - f. What was good about these groups? And what things do you think need improvement?
 - g. What were the benefits?
 - h. Were there negative experiences?
- 9. In your view, how effective were the trained volunteers at delivering the exercises and encouraging your family member to be more active?
 - a. Explore impact of the exercise programme on family members health and activity levels.
 - b. Explore positive and negative experiences of the intervention.
- 10. In your view, how effective were the trained volunteers at delivering the nutrition wheel and encouraging your family member to eat healthily?
 - a. Explore impact of the nutrition programme on family members health and eating behaviours.
 - b. Explore positive and negative experiences of the intervention.
- 11. Do you have any suggestions or comments about the intervention?
 - d. Explore things that went well
 - e. Explore things that could be improved
- 12. What are your views on your family member using online tech to access the intervention?
 - e. Explore any barriers to accessing, or using the online intervention e.g., tech knowledge, general perceptions of using technology, any misconceptions regarding online platforms, visibility and sound during sessions
 - f. Explore the things that helped / facilitated use of online tech
- 13. In your opinion, how could these volunteer-led sessions be continued and extended to other clubs?
 - a. Explore participants views on barriers and facilitators to the implementation of the intervention in other settings

Screening and Escalation Plan

Screening at the start of each support session (5-10 minutes)

- Exercise: It is essential to use Table 1 (Exercise Screening at each Session)to identify any changes in participant-specific considerations (or comorbidities)and if necessary, to take the appropriate action defined in Figure 1 (Escalation Process). Please also report any actions taken or concerns to the Frail2Fit team on (insert number here), or (insert email here).
- **Nutrition:** Any marked change in appetite, eating habits (including change inability to eat or drink) and perceived unintended weight loss: Do not exercise and notify trial team on (insert number and email here).
- **Medications:** If participant has started any new medications, report this to the Frail2Fit team. Ensure patient has taken prescribed medications as normal. If they haven't contact the Frail2Fit team on (insert number and email here).

If a concern arises please refer to the **SAFETY ESCALATION PROCESS** outlined in Figure 1.

Table 1. Exercise Screening at each Session

Has the participant been experiencing any of the following?

Delayed onset muscle soreness

If yes, observe and modify exercises accordingly

Has the participant experienced any of the following?

Contacted GP

Visited A&E

Been admitted to hospital?

If yes, please contact Frail2Fit trial team before delivering the exercise support session.

Has the participant experienced any of the following?

Fever or infection

Nausea, vomiting or diarrhea

Recent dizziness or fainting

Any new or worsening of symptoms (e.g., pain)

If yes, no exercise - alert trial team

Emergency Scenario

Chest, arm or jaw pain Dial 999

Anything that the instructor feel's is an emergency

When appropriate please alert the Frail2Fit team

Safety Escalation

Based on your screening results you may need to escalate to the trial team for further advice before proceeding with your session – if this is the case please record this in your session completion log.

There may also be circumstances where you need to escalate during or after your session as outlined in Figure 1.

Patient safety is our highest priority, so if you have any concerns or doubts, please just call us.

KEY REMINDER: Please remember to alert the trial team to **any changes** in the participants' status such as:

- New medical diagnosis or co-morbidity
- Start of new medication and removal of a medication
- Admission to hospital or visit to A&E or GP
- New investigations that have been arranged
- New onset of symptoms or worsening of previous symptoms
- Change in known co-morbidities

Figure 1. Safety Escalation Process

Low Risk

- Defined as a scenario where telephone advice is required
- Ring Frail2Fit team on (insert number here)

Intermediate Risk

- Defined as a scenario where the volunteer is unsure whether proceeding with the session is safe or requires further advice opost session. These scenarios may or may not require further action.
- Ring Frail2Fit team on (insert number here)

Emergency Scenario

- This is defined as anything the volunteer feels is an emergency
- Ring 999 or refer participant to 999 / 111 if able
- When appropriate please alert the Frail2Fit team on (insert number here)

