The NPT provides a set of sociological tools to understand and explain the social processes through which new or modified practice of thinking, enacting, and organizing work are operationalized in healthcare and other institutional settings. The use of an implementation theory is useful as it helps researchers identify, describe and explain important elements of the implementation process. The three core problems which the theory is concerned with are: implementation (bringing of a practice or practices into action), embedding (routine incorporation of practice or practices into everyday work of individuals and groups) and integration (reproduction and sustainability of a practice or practices among the social matrices of an organization or institution). NPT was used in the development of the study protocol as well as the online physical activity and nutrition intervention. The online NPT toolkit was used to assist in critically thinking through the processes and challenges which may arise in implementing and integrating an intervention in a complex health care setting. NPT was chosen as the framework that underpinned this study as it was systematic in its approach, easy to understand and provided a proven framework to evaluate the implementation process of this study. Determining the acceptability of the intervention through qualitative measures will aid future implementation studies.

Secondary outcome measures: The secondary outcomes will include the measurement of physical activity levels, physical function, appetite, well-being, anxiety and depression, and self-efficacy for managing chronic disease. These measures are detailed below and will be measured at baseline (in hospital), 3 months (via telephone) and 6 months (via telephone).

Physical activity: PA will be measured using the physical activity scale for the elderly (PASE) [59]. The PASE measures a broad spectrum of activities including leisure-time, household, and occupational PA during the previous 7 days, and has good stability and convergent validity within community-dwelling older adults [60].

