Date of device removed :						
	d d	d d	⊥ m	l m	L y	y
Total number of days :	u	u	m	m	У	У
Reason for early removal of device:						
No. of Hospital Readmissions:						

Barthel Index

Bowels incontinent (or needs to be given enema) occasional accident (once/week) continent	0 1 2
Bladder incontinent, or catheterized and unable to manage occasional accident (max. once per 24 hours) continent (for over 7 days)	0 1 2
Grooming needs help with personal care independent face/hair/teeth/shaving (implements provided)	0
Toilet Use dependent needs some help, but can do something alone independent (on and off, dressing, wiping)	0 1 2
Feeding unable needs help cutting, spreading butter, etc. 2 = independent (food provided within reach)	0
Transfer unable – no sitting balance major help (one or two people, physical), can sit minor help (verbal or physical) independent	0 1 2 3
Mobility Immobile wheelchair independent, including corners, etc. walks with help of one person (verbal or physical) independent (but may use any aid)	0 1 2 3
Dressing dependent needs help, but can do about half unaided independent (including buttons, zips, laces etc)	0 1 2
Stairs unable needs help (verbal, physical, carrying aid) independent up and down	0 1 2
Bathing dependent independent (or in shower)	0
Total Score	e:

PASE

Leisure Time Activity

- 1. Over the past 7 days, how often did you participate in sitting activities such as reading, watching TV, or doing handcrafts?
- 0) Never (go to question 2)
- 1) Seldom (1-2 days) (go to question 1a and 1b)
- 2) Sometimes (3-4 days) (go to question 1a and 1b)
- 3) Often (5-7 days) (go to question 1a and 1b)
- 1a. What were these activities?
- 1b. On average, how many hours did you engage in these sitting activities?
- 0) Less than 1 hour
- 1) 1-1.9 hours
- 2) 2-4 hours
- 3) >4 hours
- 2. Over the past 7 days, how often did you take a walk outside your home or yard for any reason? For example, for fun or exercise, walking to work, walking the dog, etc
- 0) Never (go to question 3)
- 1) Seldom (1-2 days) (go to question 2a)
- 2) Sometimes (3-4 days) (go to question 2a)
- 3) Often (5-7 days) (go to question 2a)
- 2a. On average, how many hours per day did you spend walking?
 - 0) Less than 1 hour
 - 1) 1-1.9 hours
 - 2) 2-4 hours
 - 3) >4 hours
 - 3. Over the past 7 days, how often did you engage in light sport or recreational activities such as bowling, golf with a cart, shuffleboard, fishing from a boat or pier or other similar activities?

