 - 0) Never (go to question 4)
 - 1) Seldom (1-2 days) (go to question 3a and 3b)
 - 2) Sometimes (3-4 days) (go to question 3a and 3b)
 - 3) Often (5-7 days) (go to guestion 3a and 3b)
- 3a. What were these activities?
- 3b. On average, how many hours did you engage in these light sport or recreational activities?
 - 0) Less than 1 hour
 - 1) 1-1.9 hours

- 2) 2-4 hours
- 3) >4 hours
- 4. Over the past 7 days, how often did you engage in moderate sport and recreational activities such as doubles tennis, ballroom dancing, hunting, ice skating, golf without a cart, softball or other similar activities?
- 0) Never (go to question 5)
- 1) Seldom (1-2 days) (go to question 4a and 4b)
- 2) Sometimes (3-4 days) (go to question 4a and 4b)
- 3) Often (5-7 days) (go to question 4a and 4b)
 - 4a. What were these activities?
 - 4b. On average, how many hours did you engage in these moderate sports or recreational activities?
- 0) Less than 1 hour
- 1) 1-1.9 hours
- 2) 2-4 hours
- 3) >4 hours
- 5. Over the past 7 days, how often did you engage in strenuous sport and recreational activities such as jogging, swimming, cycling, singles tennis, aerobic dance, skiing (downhill or cross-country) or other similar activities?
- 0) Never (go to guestion 6)
- 1) Seldom (1-2 days) (go to question 5a and 5b)
- 2) Sometimes (3-4 days) (go to question 5a and 5b)
- 3) Often (5-7 days) (go to question 5a and 5b)
- 5a. What were these activities?
- 5b. On average, how many hours did you engage in these strenuous sport or recreational activities?
 - 0) Less than 1 hour
 - 1) 1-1.9 hours
 - 2) 2-4 hours
 - 3) >4 hours

- 6. Over the past 7 days, how often did you do any exercises specifically to increase muscle strength and endurance, such as lifting weights or pushups, etc.?
- 0) Never (go to question 7)
- 1) Seldom (1-2 days) (go to question 6a and 6b)
- 2) Sometimes (3-4 days) (go to question 6a and 6b)
- 3) Often (5-7 days) (go to question 6a and 6b)

6a. What were these activities?

- 6b. On average, how many hours did you engage in these exercises to increase muscle strength?
 - 0) Less than 1 hour
 - 1) 1-1.9 hours
 - 2) 2-4 hours
 - 3) >4 hours

Household Activity

- **7.** During the past 7 days, have you done any light housework, such as dusting or washing dishes?
- 1) No
- 2) Yes
- 8. During the past 7 days, have you done any heavy housework or chores, such as vacuuming, scrubbing floors, washing windows, or carrying wood?
- 1) No
- 2) Yes

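### Five of the six closed PASE duration items give no time unit, so some answers can be coded two ways: a minor measurement point on a secondary outcome

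*Combined protocol and SAP*

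**What the plan says.** Section 5 of the protocol (Secondary outcome measures) makes PASE the questionnaire measure of physical activity, with a 7-day recall. It is taken in hospital at baseline and by telephone at 3 and 6 months. Quantitative data analysis, in the same section, compares baseline with both later visits.

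In the booklet, PASE items 1 to 6 share one structure. The stem asks on how many of the past 7 days an activity was done (never, 1-2, 3-4 or 5-7 days), and a follow-up then asks for its duration. All six follow-ups offer the same four answers, starting with "0) Less than 1 hour" and going on to 1-1.9, 2-4 and over 4 hours.

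The duration questions differ in one respect:

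- Item 2a (walking): "On average, how many hours per day did you spend walking".
- Item 1b (sitting): "On average, how many hours did you engage in these sitting activities".
- Item 3b (light sport): "On average, how many hours did you engage in these light sport or recreational activities".
- Item 4b (moderate sport): "On average, how many hours did you engage in these moderate sports or recreational activities".
- Item 5b (strenuous sport): "On average, how many hours did you engage in these strenuous sport or recreational activities".
- Item 6b (muscle strength): "On average, how many hours did you engage in these exercises to increase muscle strength".

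Only 2a names a period. Item 10a (paid or voluntary work) is a separate question with an open numeric answer, and it asks for hours per week. Neither the booklet nor the protocol gives a scoring rule or an interviewer instruction that supplies the unit for the other five.

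**The concern.** Two explicit units appear on the form, per day in 2a and per week in 10a, and five items have neither. The only period named near those five is the 7-day window in the stem, so a respondent can answer with a weekly total. The answer is then placed in categories that, going by item 2a, are meant for daily hours. The same behaviour can receive two codes, and the recorded answer does not show which reading was used.

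The stake is measurement error in a score used to judge change from baseline to 3 and 6 months. Item 6b is the closest of the six to the study's own resistance exercise. The protocol describes no comparison group that would help separate a change in how the item is read from a change in activity.

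**Working it through.** The plan states no figure to reproduce. The check is a count of items, followed by a coding exercise.

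**Count.** Six closed duration items share the four categories (1b, 2a, 3b, 4b, 5b, 6b). One has a unit (2a) and five do not.

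**Inputs for item 6b.** From section 5, Intervention (Exercise): 20-30 minutes per session, encouraged 2-3 times a week. From section 5, Intervention: group sessions run three times a week in weeks 1-4, twice in weeks 5-8 and once in weeks 9-12.

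**Formulas.** Hours per active day = minutes / 60. Weekly total = sessions × minutes / 60. Each result is then placed in the printed categories.

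| Pattern | Per active day | Code | Weekly total | Code |
|---|---|---|---|---|
| 3 × 30 min | 0.50 h | under 1 | 1.50 h | 1-1.9 |
| 3 × 20 min | 0.33 h | under 1 | 1.00 h | 1-1.9 |
| 2 × 30 min | 0.50 h | under 1 | 1.00 h | 1-1.9 |
| 2 × 20 min | 0.33 h | under 1 | 0.67 h | under 1 |
| 1 × 30 min | 0.50 h | under 1 | 0.50 h | under 1 |
| 1 × 20 min | 0.33 h | under 1 | 0.33 h | under 1 |

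Three of the four encouraged patterns (the first four rows) change category with the reading. The last two rows are the weekly group session of weeks 9-12, and they do not change.

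**Other items (assumed values, for illustration only).**

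- Sitting 3 h on each of 7 days: 2-4 hours per day, but 3 × 7 = 21 h and so over 4 hours as a total.
- Sitting 5 h on each of 7 days: over 4 hours either way (5 h or 35 h).
- A light activity for 1.5 h on each of 3 days: 1-1.9 hours per active day, but 3 × 1.5 = 4.5 h and so over 4 hours as a total.

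A code therefore changes only when multiplying by the number of days carries the answer over a boundary. A respondent who answers never to the stem skips the duration item.

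**The case against.** The strongest reply is that the form largely explains itself. Each stem counts days first, and the follow-up then asks for an average. An average after a count of days suggests an amount per day or per occasion, and a weekly total would count frequency twice. Where the form wants a weekly figure, in 10a, it says so. This stands, and it makes the ambiguity lopsided. It does not remove it, because the words that settle the matter in 2a are absent from the other five items.

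A reader might also infer more than the documents support:

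- *That the three-times-weekly programme is miscoded at the PASE visits.* Three group sessions a week run only in weeks 1-4. Baseline comes before the programme, the 3-month visit follows the once-weekly phase, and no group sessions are scheduled at 6 months. The 6b example rests on the encouraged 2-3 times a week, not on the group timetable.
- *That all five items shift by at least one category.* Answers that cross no boundary do not move, and those who answer never are not asked. In patients with a Clinical Frailty Scale score of 5 or more, never seems a likely answer to the moderate and strenuous sport items, although that is an inference.
- *That moving from ward to telephone will look like a change in activity.* Appendix 2 lists one staff role for all three questionnaire packs, which favours consistent handling. No script is documented, but nothing shows drift either.
- *That the unit was dropped from the published instrument.* The documents cannot show this. What they show is that the form is inconsistent with itself.

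**Conclusion.** The point holds as a minor source of measurement error. Items 1b, 3b, 4b, 5b and 6b lack a unit that a matching item on the same form carries, and nothing in the documents supplies it. For the exercise that participants are encouraged to do, three of four limiting patterns code one category higher if read as a weekly total. That result assumes the activity is reported at the protocol's stated minutes and frequency, and that some respondents answer with a 7-day total. The documents do not show how many would.

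The effect on the PASE total cannot be computed, because no item weights are given. The consequence is limited further because PASE is one of several secondary outcomes, the study states that it is not powered for outcome differences, and GENEActiv measures activity in parallel.

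**What to change.** Before first use, insert the daily unit in items 1b, 3b, 4b, 5b and 6b so that they match 2a, and read the same wording on the ward and by telephone. A one-line interviewer note could also say whether the average is over active days or all seven, since 2a itself leaves that open. For the encouraged exercise the choice makes no difference: 3 × 30 min is 0.50 h per active day, or 1.5 / 7 = 0.21 h over seven days, and both are under 1 hour.

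The cost is five small edits to the booklet. If the booklet is already in use, changing it would mix two wordings within the series. In that case the sponsor should document which reading was applied at each visit and report it with the PASE results, because answers already collected cannot be reliably recoded.
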